Name of Sponsor: Abbott Taiwan	Name of Finished Product: Hidrasec Infants Granules for Oral Suspension 10 mg Hidrasec Children Granules for Oral Suspension 30 mg	Name of Active Ingredient(s): Racecadotril

○ 4 = slight improvement of acute diarrhea, ○ 5 = no change in acute diarrhea, ○ 6 = worsening of acute diarrhea. (Treatment success = GPA score of 1 or 2).
 
 • For toilet trained children only: number of stools per day as well as number of watery stools per day from start of treatment and until end of study treatment. 
Safety and tolerability: To evaluate the safety and tolerability of Racecadotril in addition to ORS in infants and children with acute diarrhea by adverse events, physical examination and vital signs.
		

Methodology: This is a prospective, open-label, multicenter, single-arm study evaluating the efficacy and safety of Racecadotril in infants and children with acute diarrhea.
 
 
Open-label treatment
 <pre> graph LR V1[Visit 1, Day 1 Start treatment] --> T[Racecadotril + ORS] T --> V2[Visit 2, Day 6 Recovery or End of treatment] V2 --> FU[Safety Follow-up 5-7 days after V 2] </pre> 
 
Screening and Enrolment (Day 1, Visit 1) Subjects presenting with acute diarrhea will be evaluated for eligibility. They will undergo a physical examination including vital signs, a review of their medical history including vaccination history and concomitant medication. If the subjects are eligible, demographics, number of stools during the last 12 hours will be assessed as baseline values. On Day 1, the subject will start with study treatment. The starting dose will either be the noon or evening dose.
 
Treatment period (until recovery, maximally five days) Subjects will be treated with Racecadotril three times daily according to the body weight dose requirement on an out-patient basis for maximum 5 days in addition to ORS. ORS will be prescribed by the investigator. The parent(s)/caregiver(s)/legal representative(s) will be instructed to stop treatment when the patient recovered. Recovery is defined by the evacuation of the first of two consecutive normal stools or no stool within 12 hours. In the evening of each day, the parent(s)/caregiver(s)/legal representative(s) will fill in their diaries, documenting date and time of each individual stool, the stool consistency of each stool, ORS amount and the study drug intake. AEs are to be reported on an ongoing basis. Treatment will stop at recovery (last dose)
		

Name of Sponsor: Abbott Taiwan	Name of Finished Product: Hidrasec Infants Granules for Oral Suspension 10 mg Hidrasec Children Granules for Oral Suspension 30 mg	Name of Active Ingredient(s): Racecadotril
--	---	--

will be taken in the morning after recovery, ORS can be continued until Visit 2) or after the morning dose of day 6, if not recovered.

End of treatment (at recovery or Day 6, Visit 2)

The last dose of study drug intake will be the morning dose of day 6, if not recovered earlier. The parent(s)/caregiver(s)/legal representative(s) will visit the site for the end of study visit of the child. Data on vital signs, AEs, physical examination and concomitant medication will be collected. The parent(s)/caregiver(s)/legal representative(s) will return the diaries and unused medication.

Safety follow-up call (Day 11-13)

A phone call contact will be performed 5-7 days after the end of the treatment period or recovery for the safety follow-up.

Table 1. Flow Chart of Study Assessments

Period	Screening	End of Treatment period	Safety follow-up (phone call,-7 days after Visit 2)
Visit	1	2	3
Day	1	6²	11-13
Informed consent	X		
Inclusion/exclusion criteria	X		
Demographic data	X		
Medical history including vaccination history	X		
Physical examination	X	X	
Vitals signs	X	X	
Dispense study drug	X		
Concomitant medication	X	X	X
Compliance check		X	
Global physician assessment		X	
Adverse events	X	X	X

Name of Sponsor: Abbott Taiwan	Name of Finished Product: Hidrasec Infants Granules for Oral Suspension 10 mg Hidrasec Children Granules for Oral Suspension 30 mg	Name of Active Ingredient(s): Racecadotril
Collect study drug		X
Dispense diary	X ¹	
Collect diary		X

¹ Subjects' parent(s)/caregiver(s)/legal representative(s) have to fill in their daily diaries continuously.

² or within 24 hours (in exceptional justified cases within 48 hours) after recovery if this occurs before day 6

Number of Subjects (Planned):

A **maximum** number of 48 subjects will be enrolled. ***with a minimum number of 20 subjects in each age group (< 24 months of age and ≥ 24 months of age).*** Recruitment will be stopped **once 40 subjects completed the study.**

Approximately 50 subjects should be screened.

Diagnosis and Main Criteria for Inclusion:

- (1) Signed informed consent from one of the parent(s)/legal representative(s).
- (2) Subjects, both genders, aged 3 to 60 months.
- (3) Subjects with acute diarrhea (defined as the passage of three or more unformed or liquid stools within the last 24 hours and lasting for less than 3 days).

Exclusion Criteria:

- (1) Known allergy to Racecadotril or any of its ingredients.
- (2) Subjects suffering from renal or hepatic impairment.
- (3) Subjects with fever > 39 degrees Celsius
- (4) Subjects with bloody and/or purulent stools.
- (5) Subjects suffering from antibiotic (e.g. amoxicillin)-associated diarrhea, chronic diarrhea or iatrogenic diarrhea.
- (6) Subjects with alternating bouts of diarrhea and constipation.
- (7) Diarrhea due to exacerbation of chronic gastrointestinal diseases such as irritable bowel syndrome, irritable bowel disease or pancreatic exocrine insufficiency.
- (8) Cystic fibrosis or coeliac disease.
- (9) Subjects suffering from prolonged or uncontrolled vomiting.
- (10) Subjects with rare hereditary problems of fructose intolerance, glucose-galactose malabsorption syndrome or sucrase isomaltase insufficiency.
- (11) Subjects having received antibiotic treatment within 2 weeks prior to the current diarrhea event.
- (12) Subjects having received antidiarrheal drugs (except pre-or probiotics see section 7.7) 48 hours prior to Day 1.
- (13) Subjects with severe dehydration requiring intravenous fluid, electrolyte replacement or hospitalization treatment
- (14) Subject with a history of angioedema or who had reported angioedema with angiotensin converting enzyme inhibitors (such as captopril, enalapril, lisinopril, perindopril,

Name of Sponsor: Abbott Taiwan	Name of Finished Product: Hidrasec Infants Granules for Oral Suspension 10 mg Hidrasec Children Granules for Oral Suspension 30 mg	Name of Active Ingredient(s): Racecadotril

ramipril)
 
(15) Subjects with combined diseases or medical situations that would prevent to be enrolled into the study, depending on the judgment of the investigator
 
(16) Intake of experimental drug within 30 days prior to study start.
 
(17) Subjects with contraindications to ORS or susceptible to the warnings of ORS.
		

Test Product, Dose and Mode of Administration:
 
Racecadotril Infants Granules for Oral Suspension 10 mg Racecadotril Children Granules for Oral Suspension 30 mg
 
1.5 mg/kg of Racecadotril will be administered, 3 times daily, via the oral route.
 
In infants less than 9 kg: one 10 mg sachet 3 times daily. In infants from 9 kg to < 13 kg: two 10 mg sachets 3 times daily. In children from 13 kg to 27 kg: one 30 mg sachet 3 times daily. In children of more than 27 kg: two 30 mg sachets 3 times daily.
 
Racecadotril will be given three times daily in addition to standard treatment ORS. For concomitant medication (please see section 7.7).
 
Standard treatment is oral rehydration solution (ORS) according to the registered local label and the instruction of the investigator. At the start of the trial, alignment will be reached on the understanding of treatment of standard ORS with the principal investigator with the aim to use the same brand of ORS and the same age-appropriate standardized treatment pattern for the subjects throughout the trial.
		

Duration of Treatment:
 
The first dose of Racecadotril will be taken on day 1, either noon, or evening dose. The treatment duration lasts until recovery (last dose in the morning after recovery), maximally 5 days, until the morning dose of day 6.
		

Criteria for Evaluation:
 
Efficacy:
 
Primary Efficacy Variable: Duration of diarrhea (hours) between the start of treatment until last diarrheal/watery stool before recovery or end of study treatment (treatment duration maximal 5 days). Duration of diarrhea is defined as date and time of the evacuation of the final watery/diarrheal stool before recovery
		

Name of Sponsor: Abbott Taiwan	Name of Finished Product: Hidrased Infants Granules for Oral Suspension 10 mg Hidrased Children Granules for Oral Suspension 30 mg	Name of Active Ingredient(s): Racecadotril

derived from the daily diary.
 
Secondary Efficacy Variables:
 
 • Time until recovery, defined as date and time of the evacuation of the first of two consecutive normal stools or no stool within 12 hours after the first normal stool. • Number of recovered subjects in total and until each individual treatment day. Mean and median time until recovery. • Global Physician Assessment (GPA) at the end of treatment (at the discretion of the investigator): 
 ○ 1 = Complete relief of acute diarrhea, ○ 2 = marked improvement of acute diarrhea, ○ 3 = moderate improvement of acute diarrhea, ○ 4 = slight improvement of acute diarrhea, ○ 5 = no change in acute diarrhea, ○ 6 = worsening of acute diarrhea. (Treatment success = GPA score of 1 or 2). • For toilet trained children only: number of stools per day as well as number of watery stools per day from start of treatment and until end of study treatment. 
Safety: Adverse events, vital signs, physical examination.
		

Statistical Methods:
 
Efficacy: In order to compare the primary efficacy parameter, duration of diarrhea between the treatment groups a Kaplan Meier analysis will be performed. The primary efficacy parameter, duration of diarrhea, will be analyzed using descriptive statistics. In addition, a Kaplan-Meier plot will be generated for which summary statistics will be presented as well. Secondary efficacy parameters will be analyzed similarly. All parameters will be summarized using descriptive statistics.
 
Safety: The safety sample will be used for the analysis of the safety and tolerability data. Treatment emergent AEs are summarized. Severity and drug-event relationship of treatment emergent AEs are summarized separately. Vitals signs, including changes from baseline will be
		

Name of Sponsor: Abbott Taiwan	Name of Finished Product: Hidrasec Infants Granules for Oral Suspension 10 mg Hidrasec Children Granules for Oral Suspension 30 mg	Name of Active Ingredient(s): Racecadotril

summarized. A frequency table will be presented for markedly abnormal values.
 
Sample size
 
In total, 40 subjects will be allocated to receive Racecadotril treatment, 20 subjects in each age group (< 24 months of age and ≥ 24 months of age). Results of a recently finalized study in Russian children showed that all children under Racecadotril treatment recovered within 3 days of drug treatment. A sample size of 40 subjects is sufficient to estimate a two-sided 95% confidence interval with the precision of 3.1 percentage points for a recovery of at least 99% of the subjects after 3 days of Racecadotril treatment. In order to account for drop-outs, maximum 48 subjects will be recruited. Recruitment will be stopped once 40 subjects have completed the study.
		

TABLE OF CONTENTS

CLINICAL STUDY PROTOCOL	1
SYNOPSIS.....	2
TABLE OF CONTENTS	9
LIST OF ABBREVIATIONS AND DEFINITION OF TERMS.....	12
1 ETHICS.....	14
1.1 Independent Ethics Committee or Institutional Review Board	14
1.2 Ethical Conduct of the Study	14
1.3 Subject Information and Consent.....	14
2 INTRODUCTION.....	16
3 STUDY OBJECTIVES.....	17
3.1 Primary Objective(s)	17
3.2 Secondary Objective(s)	17
3.3 Safety Objective(s).....	17
4 STUDY DESIGN.....	18
4.1 Overall Study Design and Plan-Description	18
4.2 Discussion of Study Design, Including the Choice of Control Groups	19
5 SELECTION OF STUDY POPULATION.....	20
5.1 Inclusion Criteria.....	20
5.2 Exclusion Criteria	20
6 REMOVAL OF SUBJECTS FROM THERAPY OR ASSESSMENT.....	21
7 TREATMENTS.....	23
7.1 Treatments to Be Administered	23
7.2 Packaging and Labeling	23
7.3 Storage and Dispensing of Study Drug.....	24
7.4 Method of Assigning Subjects to Treatment Groups.....	24
7.5 Selection of Doses and Timing in the Study	24
7.6 Blinding and Treatment Code Information	24
7.7 Prior and Concomitant Therapy	25
7.8 Treatment Compliance	26

8	STUDY ASSESSMENTS AND FLOW CHART	27
8.1	Efficacy Measurements	27
8.2	Safety Measurements	27
8.3	Other Assessments	28
8.4	Appropriateness of Measurements	29
8.5	Primary Efficacy/ Variable(s)	29
8.6	Flow Chart of Study Assessments	29
9	ADVERSE EVENTS.....	31
9.1	Adverse Events	31
9.1.1	Recording of Adverse Events	31
9.1.2	Follow-up of Adverse Events	33
9.2	Serious Adverse Events (SAEs).....	33
9.2.1	Reporting Serious Adverse Events	34
9.3	Pregnancy.....	34
10	STATISTICAL METHODS AND DETERMINATION OF SAMPLE SIZE	35
10.1	General Definitions and Conventions	35
10.2	Subject Samples	36
10.3	Efficacy	37

1 ETHICS

1.1 Independent Ethics Committee or Institutional Review Board

The Sponsor (or an authorized representative) or the Investigator (according to national provisions) is responsible for obtaining written approval for the clinical study protocol (including all substantial protocol amendments), the written subject informed consent form (including written assent, when applicable), informed consent updates, subject recruitment procedures (e.g., advertisements) and any other written information to be provided to subjects from an Independent Ethics Committee (IEC) / Institutional Review Board (IRB) that complies with the local regulatory requirements.

Written approval of the study must be obtained from the IEC/IRB prior to the study being implemented (i.e., shipment of clinical supplies to the Investigator or screening of subjects). Copies of the approval documentation will be maintained by both the Investigator and the Sponsor (or an authorized representative) in the designated study documentation files.

The Sponsor (or an authorized representative) or the Investigator (according to national provisions) will submit written reports of the clinical study status to the IEC/IRB annually, or more frequently if requested by the IEC/IRB. A final study notification should be forwarded to the IEC/IRB within 90 days after the study has completed, or in the event of premature termination of the study, within 15 days with the rationale for study termination clearly explained. Copies of all clinical study status reports (including termination) will be maintained by both the Investigator and the Sponsor (or an authorized representative) in the study documentation files.

In accordance with national provisions and the rules of the EU Clinical Trial Directive, the Sponsor (or an authorized representative) will inform all participating IECs/IRBs and national authorities of all SAEs/SADRs/SUSARs or other safety-related information, which occur during the clinical study.

1.2 Ethical Conduct of the Study

Good Clinical Practice (GCP) is an international ethical and scientific quality standard for designing, conducting, recording, and reporting studies that involve the participation of human subjects. The study will be conducted in compliance with GCP and the applicable national regulations to assure that the rights, safety, and wellbeing of the participating study subjects are protected consistent with the ethical principles that have their origin in the Declaration of Helsinki.

1.3 Subject Information and Consent

Voluntary written informed consent will be obtained from one parent/legal representative of each subject prior to performing any study-related procedures. Each parent/legal representative will be given both verbal and written information describing the nature and duration of the clinical

study. The informed consent process will take place under conditions where the parent/legal representative has adequate time to consider the risks and benefits associated with the child's participation in the study. Subjects will not be screened or treated until the parent/legal representative has signed an approved informed consent written in a language that is understandable to the subject's parent/legal representative.

The IEC/IRB approved informed consent form will be signed and personally dated by the parent/legal representative and the person who conducted the informed consent discussion. Each parent/legal representative is to receive a copy of the signed and dated written informed consent form and any other written subject information.

The signature of an impartial witness is to be obtained in the event the subject or the subject's legally acceptable representative is unable to read. Additional signatures on the informed consent form may be required in accordance with IEC/IRB requirements or those of the Sponsor (or an authorized representative).

The Investigator is responsible for assuring the appropriate content of the informed consent form and that informed consent is obtained from each parent/legal representative in accordance with the applicable regulations and guidelines. The original signed informed consent is to be retained in the study documentation files.

The Investigator shall maintain a log of all parent(s)/legal representative(s) who sign the informed consent form and indicate if the subject received study drug or, if not, the reason why. The subject's medical records should also document that the informed consent form was signed and dated prior to any study-related procedures being performed.

2 INTRODUCTION

Racecadotril (acetorphan), an enkephalinase inhibitor, represents a promising approach to the treatment of diarrhea. Water and electrolyte transport in the intestinal mucosa is regulated by local messengers (neuropeptides, amines, and eicosanoids). Most of them act via the mediation of cyclic adenosine monophosphate (cAMP), activating or inhibiting its production from adenosine triphosphate. An increase in cAMP is induced by endogenous (e.g. VIP, PGE2) or exogenous agents (e.g. V. cholerae, E. coli toxins) and leads to net hypersecretion of water and electrolytes. Opiate neuropeptides are localized in the intestine myenteric and submucosal plexuses, where they modulate motility (mu receptors) and secretion (delta receptors). Activation of mu receptors prolongs intestinal transit while activation of delta receptors reduces intestinal secretion of water and electrolytes. Enkephalins activate delta receptors and inhibit adenylyclase, thus facilitating a decrease in cAMP levels with a consequent reduction in water and electrolyte secretion. This anti-secretory action, however, is brief because enkephalins are rapidly degraded by the membrane peptidase enkephalinase (EC 3.4.24.11). Racecadotril is a prodrug that is rapidly hydrolysed in man into the active metabolite thiorphan, which is a powerful and selective enkephalinase inhibitor. Thus, the anti-secretory action of enkephalins is prolonged in the presence of thiorphan. Furthermore, unlike opiates and loperamide, Racecadotril does not act on mu receptors and therefore it does not prolong intestinal transit, nor does it favour bacterial growth in the small intestine. Racecadotril is devoid of any central or peripheral nervous side effect, at the opposite of opiates, such as respiratory depression or inhibition of intestinal transit.

Diarrhea is defined as the passage of unusually loose or watery stools, with a frequency of at least three times in a 24-hour period. The objective for treatment of acute diarrhea associated symptoms is to prevent and treat dehydration at first, to prevent nutritional damage and to reduce the duration and severity of diarrhea. Antidiarrheal drugs have been developed to prevent dehydration and to resolve diarrhea on top of with oral rehydration solution (ORS). Ideally antidiarrheal has a positive safety profile and have limited or no effects on motility and basal intestinal secretion.

[REDACTED]

3 STUDY OBJECTIVES

3.1 Primary Objective(s)

The primary objective is to evaluate the efficacy of Racecadotril in addition to standard treatment oral rehydration solution (ORS) in infants and children (3 months until 60 months) with acute diarrhea measured as duration of diarrhea (hours) between the start of treatment until final watery/diarrheal stool before recovery or end of study treatment (treatment duration maximal 5 days).

Duration of diarrhea is defined as date and time of the evacuation of the final watery/diarrheal stool before recovery derived from the daily diary.

3.2 Secondary Objective(s)

- Time until recovery, defined as date and time of the evacuation of the first of two consecutive normal stools or no stool within 12 hours after the first normal stool.
- Number of recovered subjects in total and until each individual treatment day.
- Global Physician Assessment (GPA) at the end of treatment (at the discretion of the investigator):
 - 1 = Complete relief of acute diarrhea,
 - 2 = marked improvement of acute diarrhea,
 - 3 = moderate improvement of acute diarrhea,
 - 4 = slight improvement of acute diarrhea,
 - 5 = no change in acute diarrhea,
 - 6 = worsening of acute diarrhea.(Treatment success = GPA score of 1 or 2).
- For toilet trained children only: number of stools per day as well as number of watery stools per day from start of treatment and until end of study treatment.

3.3 Safety Objective(s)

To evaluate the safety and tolerability of Racecadotril together with oral rehydration solution (ORS) in infants and children (3 months until 60 months) with acute diarrhea by adverse events, physical examination and vital signs.

4 STUDY DESIGN

4.1 Overall Study Design and Plan-Description

This is a prospective, open-label, multicenter, single-arm study evaluating the efficacy and safety of Racecadotril in infants and children with acute diarrhea in out-patients. The number of subjects to be screened is 50 in order to achieve 40 subjects treated with standard treatment (oral rehydration solution, ORS) plus Racecadotril.

1.5 mg/kg of Racecadotril will be administered, 3 times daily, via the oral route. Study drug intake will start either with the noon or evening dose on day 1.

In infants less than 9 kg: one 10 mg sachet 3 times daily.

In infants from 9 kg to <13 kg: two 10 mg sachets 3 times daily.

In children from 13 kg to 27 kg: one 30 mg sachet 3 times daily.

In children of more than 27 kg: two 30 mg sachets 3 times daily.

Standard treatment is oral rehydration solution (ORS) according to the registered local label and the instruction of the investigator. At the start of the trial, alignment will be reached on the understanding of treatment of standard ORS with the principal investigator with the aim to use the same brand of ORS for the subjects throughout the trial. ORS treatment will be documented in the CRF.

Screening and Enrolment (Day 1, Visit 1)

Subjects presenting with acute diarrhea will be evaluated for eligibility. They will undergo a physical examination including vital signs, a review of their medical history including vaccination history and concomitant medication. If the subjects are eligible, demographics, number of stools during the last 12 hours will be assessed as baseline values. On Day 1, the subject will start with study treatment. The starting dose will either be the noon, or evening dose depending on the timing of Visit 1.

Treatment period (until recovery, maximally 5 days)

Subjects will be treated with Racecadotril three times daily according to the body weight dose requirement on an out-patient basis for maximum 5 days. The subjects will be treated with ORS (according to the registered local label and the instruction of the investigator) in addition to Racecadotril. ORS will be prescribed by the investigator and will be taken according to the product label and the instruction of the investigator. The parent(s)/caregiver(s)/legal representative(s) will be instructed to stop study drug treatment when the patient recovered. On each day, the parent(s)/caregiver(s)/legal representative(s) will fill in their diaries, documenting the date and time of each individual stool, the stool consistency of each stool (diarrheal/watery or normal), the amount of ORS, and the study drug intake. After the occurrence of two consecutive normal stools or no stool within 12 hours, the parent(s)/caregiver(s)/legal representative(s) can stop recording of the diary and return to the study site for the end of treatment visit. The date of recovery is the day when the first of two consecutive normal stools were excreted or the day

[figure not shown]
when no stool within 12 hours after the first normal stool was observed. AEs are to be reported on an ongoing basis.

End of treatment (Day 6 or early recovery, Visit 2)

The last dose of study drug will be the morning dose of day 6, if not recovered earlier (last dose will be the morning dose after recovery, ORS can be continued until Visit 2). On the same day, or within 24 hours after recovery (in exceptional cases within 48 hours), the parent(s)/caregiver(s)/legal representative(s) will visit the site for the end of treatment visit of the child. Data on vital signs, AEs, physical examination and concomitant medication will be collected. Subjects will return their diaries and unused medication.

Safety follow-up

A phone call will be performed 5-7 days after the end of the treatment period for the safety follow-up.

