4.2 Discussion of Study Design, Including the Choice of Control Groups

[Redacted content]

5 SELECTION OF STUDY POPULATION**5.1 Inclusion Criteria**

- (1) Signed informed consent from one of the parent(s)/legal representative(s).
- (2) Subjects, both genders, aged 3 to 60 months.
- (3) Subjects with acute diarrhea (defined as the passage of three or more unformed or liquid stools within the last 24 hours and lasting for less than 3 days).

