8.3 Other Assessments

Informed Consent

Voluntary written informed consent must be obtained from one parent/legal representative prior to performing any study-related procedures (see Section 1.3).

Demographic Data

Demographic data (gender, age, year and month of birth, race) will be collected for all subjects.

Medical History

Any clinical event, including diagnosis, condition, or surgery, that occurred prior to allocation to treatment, is to be recorded on the Medical History form. In case a clinical event concerns a chronic disorder, which means it started in the past and it is still present at the screening visit, it should also be recorded on the Medical History Form. Examples of these events are diabetes, migraine, and hay fever.

Concomitant Medication

All medication taken by the subject during the study (from signing the informed consent form through post-study follow-up) is to be recorded on the Concomitant Medication form, except for study drug.

Subject Diary

The parent(s)/caregiver(s)/legal representative(s) have to document date and time of each individual stool of the subject and the stool consistency (watery, normal) of each evacuation continuously. The subject individual stool consistency before start of the diarrhea is defined as normal (e.g. taking into account the age and diet, e.g. breast feeding, of the individual subject).

Recording can be stopped after the excretion of two consecutive normal stools or no stool within 12 hours.

The date, time and dose of study drug intake as well as the amount ORS consumed has to be recorded.

Fever will be measured twice daily, once in the morning and once in the evening with at least 12-hour interval using the same device and method (preferably ear temperature), by the parent(s)/caregiver(s)/legal representative(s) and documented in the diary including method, time and value.

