10.3 Efficacy

The primary efficacy variable is the duration (hours) of diarrhea (treatment duration max 5 days). Duration of diarrhea is defined as date of the evacuation of the last watery/diarrheal stool before recovery or end of treatment.

The primary parameter, duration of diarrhea, will be analyzed using descriptive statistics. In addition, a Kaplan-Meier plot will be generated for which summary statistics will be presented as well.

The secondary efficacy variables are

- Time until recovery, defined as date and time of the evacuation of the first of two consecutive normal stools or no stool within 12 hours after the first normal stool.
- Number of subjects recovered; in total and until each individual treatment day
- Mean and median time until recovery
- Assessment of treatment success by the physician:
The assessment of treatment success by the physician will be done using the Global Physician Assessment.

GPA score:

- 1 = Complete relief of acute diarrhea,
- 2 = marked improvement of acute diarrhea,
- 3 = moderate improvement of acute diarrhea,
- 4 = slight improvement of acute diarrhea,
- 5 = no change in acute diarrhea,
- 6 = worsening of acute diarrhea.

Treatment will be rated as success when the GPA score equals 1 or 2.

- Number of stools at baseline and per treatment day for toilet-trained subjects, only.
- Number of watery stools per day for toilet-trained subjects, only.

Secondary efficacy parameters will be analyzed similarly to the primary analysis. All parameters will also be summarized using descriptive statistics.

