10.8 Determination of Sample Size

In total, 40 subjects will be allocated to receive Racecadotril treatment, ~~20 subjects in each age group (< 24 months of age and \geq 24 months of age)~~. Results of a recently finalized study in Russian children showed that all children under Racecadotril treatment recovered within 3 days of drug treatment. A sample size of 40 subjects is sufficient to estimate a two-sided 95% confidence interval with the precision of 3.1 percentage points for a recovery of at least 99% of the subjects after 3 days of Racecadotril treatment. In order to account for drop-outs maximum 48 subjects will be recruited. **Recruitment will be stopped once 40 subjects have completed the study.**

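### Baseline stool count covers 12 hours but treatment counts are per day: under the SAP's change-from-baseline default, a full day shows about +100% at an unchanged stool rate

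*Protocol*

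**What the plan says.** **Baseline.** At Visit 1, Protocol 4.1 states: "number of stools during the last 12 hours will be assessed as baseline values". The synopsis agrees. This is a count of all stools. SAP 5.2 takes the last non-missing value before the first dose as baseline and mentions no rescaling.

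**Treatment.** Protocol 10.3 includes this secondary variable: "Number of stools at baseline and per treatment day for toilet-trained subjects, only". SAP 9.2.4 summarises stools and watery stools per day for toilet-trained children (Table 14.2.4; by age group, Table 14.2.9). SAP 9.2.5 adds tables, not limited to toilet-trained children, with totals and a breakdown by study day (Tables 14.2.5 and 14.2.10).

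**Summary rule.** SAP 4.1 says quantitative variables are to be described both as observed and as change from baseline. SAP 9.2.4 and 9.2.5 mention neither baseline nor change. SAP 11.2, on vital signs, names change explicitly.

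**Length of a day.** SAP 5.2 numbers days from the day of first dosing and says time-related variables will be windowed, but gives no window for stool counts. On Day 1, Protocol 4.1 says: "The starting dose will either be the noon, or evening dose depending on the timing of Visit 1". At the other end: "The last dose of study drug will be the morning dose of day 6, if not recovered earlier". The diary (Protocol 8.3) must "document date and time of each individual stool of the subject and the stool consistency (watery, normal) of each evacuation continuously", but "Recording can be stopped after the excretion of two consecutive normal stools or no stool within 12 hours".

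**The concern.** The two counts that Protocol 10.3 lists together cover different lengths of time, and no passage reconciles them. A reader of the table would naturally compare the baseline row with the daily rows, and a programmer following SAP 4.1 could subtract one from the other. On a full day the subtraction hides improvement. On a short day it can invent it.

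Nothing else in the plan supplies a matching baseline. The eligibility criterion in Protocol 5.1 does use 24 hours, but it is a threshold, "three or more unformed or liquid stools within the last 24 hours", and leaves formed stools out. The diary is dispensed at Visit 1 (flow chart, Protocol 8.6), so it holds no timed stools from before that visit.

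At stake is the reading of one descriptive efficacy table and its age-group version in a single-arm study.

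**Working it through.** **The plan's own figures.** The documents give no figure for change in stool count. Their one calculated design figure is the precision of 3.1 percentage points with 40 subjects for "a recovery of at least 99% of the subjects after 3 days of Racecadotril treatment". It reproduces as 1.96 × √(0.99 × 0.01 / 40) = 0.0308, or 3.1 points. Stool counts do not enter it, so the sample size does not depend on this point.

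**Inputs.** Baseline window 12 hours (Protocol 4.1). Treatment unit one day, nominally 24 hours (Protocol 10.3, SAP 9.2.4). Change from baseline as the default (SAP 4.1). The stool rate, its spread over the day and the clock times of doses are not given and are assumed below.

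**Step 1: full day, no true change.** Let r be the rate per 24 hours, evenly spread. Baseline is r/2, a full treatment day is r, and the displayed change is (r - r/2)/(r/2) = +100% for any r.
- r = 3: 1.5 becomes 3.
- r = 6: 3 becomes 6.

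**Step 2: full day, true fall f.** The displayed change is 2(1 - f) - 1.

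| True fall | Displayed change |
|---|---|
| 0% | +100% |
| 25% | +50% |
| 50% | 0% |
| 75% | -50% |

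**Step 3: uneven spread over the day.** Let s be the share of the day's stools that falls in the baseline window (assumed). With no true change, the display is (1 - s)/s. The true fall that displays as zero is 1 - s.

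| s | False change | True fall shown as zero |
|---|---|---|
| 0.4 | +150% | 60% |
| 0.5 | +100% | 50% |
| 0.6 | +67% | 40% |

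**Step 4: part-days.** With h hours counted and a constant rate, the display is h/12 - 1. If a day is a calendar day, Day 1 is cut short by the noon or evening start. With assumed dose times:
- Noon dose at 11:00 to 13:00 leaves 13 to 11 hours: +8% to -8%.
- Evening dose at 17:00 to 20:00 leaves 7 to 4 hours: -42% to -67%.

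The recovery day and Day 6 can also be short, with the same kind of effect.

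**Step 5: what a correction must do.** Doubling the baseline alone gives h/24 - 1. That is 0% on a full day but -50% when 12 hours are counted and -75% when 6 hours are counted. Expressing both counts per the same number of observed hours gives 0% at a constant rate on full days, and on part-days whose length does not depend on the stools themselves.

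**The case against.** The strongest reply is that no one has asked for change from baseline in stool counts. SAP 9.2.4 and 9.2.5 do not mention it, SAP 2.2 and 3.6 describe the variable only from start to end of treatment, and SAP 11.2 shows that the authors name change where they want it. This stands as a limit: the percentages above apply only if the general default in SAP 4.1 is followed. It does not remove the point, because Protocol 10.3 still lists the baseline with the daily counts, and the two rows are not comparable as they stand. The table layouts are not available here, so the row may already carry a 12-hour label.

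A reader might infer that every change from baseline would be inflated by about 100%. The documents do not support that. The figure needs a full 24-hour day and an evenly spread rate. The numbering in SAP 5.2 reads most naturally as calendar days, although no rule for stool counts is given. On that reading Day 1 is always partial and the recovery day can be. With nearly all children expected to recover after 3 days, the full days would be mainly Day 2 and perhaps Day 3.

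A reader might also infer that, in a single-arm study, baseline is the only internal reference for stool counts. It is not: full treatment days can be compared with each other in the same unit.

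The scope is also small. Protocol 10.3 pairs a baseline with total stools only, in toilet-trained children only. Watery stools have no listed baseline.

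**Conclusion.** The point holds, as a minor one. The only baseline total-stool count covers 12 hours, the treatment counts are per day, and nothing in either document brings them to a common unit. If the SAP 4.1 default is applied, a full 24-hour day shows about +100% with no true change, and a true 50% fall shows as none. This rests on a constant, evenly spread rate; with 40% to 60% of daily stools in the baseline window (assumed), the false change is +150% to +67%. Part-days behave differently and can show a false fall. Their size depends on dose times that the documents do not give.

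The effect is limited to Tables 14.2.4 and 14.2.9, and to 14.2.5 and 14.2.10 only if those show a baseline. No test or success rule uses the variable. The primary endpoint, duration of diarrhea, runs from the start of treatment and does not use the baseline count.

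**What to change.** In SAP 9.2.4 and 9.2.5, add a sentence that exempts stool counts from the change-from-baseline default in SAP 4.1 and labels any baseline row as a 12-hour count. This costs one line of text and no data.

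If a comparison with baseline is wanted, say so in those sections and express both counts per the same number of observed hours, for example per 12 hours, using the stool times already in the diary. Flag part-days (Day 1, the recovery day, Day 6), because their observed time is short and on the recovery day may end at a moment set by the stools themselves. State that the rescaling assumes stools are spread evenly over day and night. That assumption is the small downside. The work is a re-derivation from recorded times, and the SAP 5.2 day numbering can stay as it is.
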